**Methodology and Evaluations**

Depot. Newly enrolled subjects will receive the third Ovarest dose (Treatment “D”) that will be administered in the same fashion as Treatment “B”. Assessments of the PD profile of treatment “D” will also mimic evaluations of Treatment “B”. However, unlike other Ovarest groups, Treatment “D” will not have comprehensive assessments of the PK profile. The subjects that have already participated in this study may be invited to receive Treatment “D” if they are eligible per the study inclusion and exclusion criteria. The subjects in Treatments “A”, “B”, and “C” will start dosing (Treatment Day 1) on either Day 1 up to Day 4 of their menstrual cycle, or within the last 11 days of their menstrual cycle. (Note: onset of menstrual period is considered as day 1 of the menstrual cycle.) Please see Appendix G for a table of acceptable days for initiation of dosing in relation to cycle length. Permissible time windows for the start of the dosing will be determined based on the onset of menstrual period prior to the screening visit or a projected start of the next menstrual cycle. The projected start of the next menstrual cycle will be based on the date of onset of menses during the screening period and the typical length of the normal menstrual cycle for each subject as reported by each subject during the screening visit. Subjects enrolled to the third oral dose (Treatment “D”) will have a dosing initiation visit scheduled 5-9 days before the anticipated start of their next menstrual cycle, based on their self-reported menstrual cycle length and the day the current menstrual cycle began. The 4-mg qd oral dose will be administered once daily, in the morning, on an empty stomach; the 4-mg and 10-mg bid oral doses will be administered twice daily, in the morning and in the evening, 12 hours apart and on an empty stomach. Note: On an empty stomach means that the oral doses are administered at least 2 hours before or at least 2 hours after the meal. Oral administration instructions are applicable to both on-site and at-home dosing. For at-home dosing, each subject will take the oral dose with approximately 240 mL of water. Subjects randomized to the two oral doses (Treatments “A” and “B”) will have twenty-four (24) serial serum samples drawn on Treatment Days 1 and 28 immediately prior to dosing (0 time), and at 0.5, 1, 1.5, 2, 2.5, 3, 3.5, 4, 4.5, 5, 6, 7, 8, 10, 12, 13, 14, 15, 16, 17, 18, 20, and 24 hours following oral dosing. For the IM injection (Treatment “C”), serial serum samples will also be drawn on Treatment Day 1, prior to dosing (0 time), at 0.5, 1, 2, 6, 12, 18, and 24 hours postdosing. Blood samples for the IM injection will also be taken in the morning on Day 29. Additional blood samples for all subjects will be taken in the morning (in the oral groups, just prior to dosing) on Treatment Days 8, 15, and 22. Samples will be appropriately stored until they can be assayed for leuprolide and hormonal levels. Serum concentrations of luteinizing hormone (LH) and follicle-stimulating hormone (FSH), and plasma concentrations of E2 and progesterone will be measured (immediately prior to dosing) on Treatment Days 1, 8, 15, 22, and in the morning of Day 29.

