Pharmacodynamic (PD) Parameters	
As noted earlier, PD assessments include LH, FSH, E2, and progesterone.
 
Blood draws for the PD assessments will be performed immediately prior to dosing on Treatment Days 1, 8, 15, 22, and Postdosing Day 1.
 
Additional PD assessments will be performed during the follow-up visits (postdosing Days 7, 14, 21 and 28).
 
The primary PD metric - suppression of E2 level - will be assessed at each on-treatment evaluation timepoint. Treatment Day 22 and Treatment Day 28 evaluations (separately and combined) will be considered as most important. In addition to a primary E2 suppression threshold (E2 ≤ 40pg/mL), a suppression of E2 below 20 pg/mL may also be assessed, if considered necessary. The suppression of ovulation (as evidenced by progesterone levels <3 ng/mL) will be evaluated with Treatment Day 22 and Postdosing Day 1 assessments positioned as primary.
 
Similar summaries will be provided for the follow-up visits (postdosing Days 7, 14, 21, and 28). In addition, time to return to prestudy baseline hormonal levels could be estimated.
 
Number of vaginal (menstrual) bleeding days will be summarized by treatment group for 28 days of therapy and for 28 days of poststudy follow-up. The subject incidence of the onset of menstrual period after completion of therapy will be reported for each treatment group.
 
Summaries of PD metrics may be further stratified by the cycle period (days) of the start of dosing.

Safety Evaluations and Adverse Events	
Safety evaluations will be based on the discontinuations due to treatment-emergent adverse events (TEAEs), changes from screening to last assessment (poststudy) in physical and gynecological examinations, clinical laboratory test results (hematology, serum chemistry, and urinalysis), treatment-induced changes in vital signs, and by the incidence and severity of TEAEs reported. TEAEs will be reported for the entire study and separately for the two study subperiods (a 28-day dosing cycle and a 28-day postdosing evaluation period). Clinically notable events (including possible flare-up symptoms) may also be recorded on diary cards.

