### **Screening Visit**

Subjects will be assessed for eligibility within 40 days prior to the start of study medication. Written informed consent must be obtained prior to the performance of any study procedures. For eligibility purposes, abnormal laboratory or vital signs results may be repeated once if abnormal result is observed at the initial reading. Moreover, abnormalities found in the ECG may need to be confirmed by repeated measurements.

The following procedures will be performed and information collected at the Screening Visit:

- Informed Consent Form signed. Demographic data (race, age), information regarding smoking habits and alcohol consumption
- Baseline characteristics and vital signs (height, body weight, body mass index [BMI], temperature, pulse rate, respiratory rate, systolic and diastolic blood pressure)
- Relevant medical history with focus on reproductive history (number of pregnancies and deliveries), gynecological history, menstrual pattern (typical duration of a menstrual cycle and typical duration of a menstrual period), and use of contraceptives.
- Date of onset of the last menstrual period (LMP)
- Cervical cytology Papanicolaou (Pap) smear. The cervical smear may be waived if done within last 12 months and a report is available.
- Clinical laboratory tests (hematology, clinical chemistry, serology and urinalysis – see APPENDIX E for details)
- Serum pregnancy test ( $\beta$ -human chorionic gonadotropin [ $\beta$ -hCG]). Subjects with positive results are not eligible for the study.
- Alcohol breath test
- Obtain baseline PD blood sample (LH, FSH, E2, and progesterone)
- Urine drug screen and urine cotinine. Subjects with positive results are not eligible for the study.
- Physical examination
- Gynecological examination (including manual breast exam)
- 12-lead ECG
- Check of inclusion/exclusion criteria

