**Treatment Day 1 – Treatment “D”**

This visit will take place within 40 days of the Screening Visit. Subjects enrolled to the third oral dose (Treatment “D”) will have a dosing initiation visit scheduled 5-9 days before the anticipated start of their next menstrual cycle, based on their self-reported menstrual cycle length and the day the current menstrual cycle began.

- Verify no change in subject’s health status before dosing.
- Perform urine pregnancy test; subjects with positive results cannot be enrolled in the study.
- Collect samples for urine drug screen and urine cotinine tests.
- Perform alcohol breath test.
- Assign randomization number.
- Obtain baseline PK blood sample immediately (within 10 minutes) prior to dosing.
- The fasting period will be -2h to +2h for the first administered dose.
- Obtain baseline PD blood sample (LH, FSH, E2, and progesterone) immediately (within 30 minutes) prior to dosing.
- Administer study drug in the morning. Oral tablets will be administered with 240 mL of water. Perform mouth check following oral tablet dosing to ensure compliance.
- Assess body weight and vital signs (temperature, pulse rate, respiratory rate, systolic and diastolic blood pressure) predose (within 2 hours prior to dosing). Note: The vital signs will be assessed prior to the first oral dosing
- Record adverse events (AEs) and concomitant medication use.
- Release subject from the clinical site 2 hours after dosing.

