## **8. ELIGIBILITY CRITERIA**

### **8.1 Inclusion Criteria**

Subjects enrolled in this study will be members of the community at large. The recruitment advertisements may use various media types (*eg*, radio, newspaper). Subjects must meet all of the following criteria to be included in the study:

- 1) Healthy premenopausal female volunteers, aged 18 to 49 years
- 2) BMI  $\geq 18$  and  $\leq 32$  kg/m^2, and weight  $\geq 110$  lb ( $\approx 50$  kg).
- 3) Regular menstrual cycles with a usual length ranging from 21 days to 35 days. If subject has recently used hormonal birth control, historical data prior to use will be used to determine qualification and must also meet this criterion.

- 4) If of childbearing potential and sexually active with a risk of pregnancy, willing to use one of the following acceptable methods of contraception throughout the study and for at least 30 days after the last drug administration:
  - a) intrauterine contraceptive device without hormone release system placed at least 4 weeks prior to the first study drug administration with simultaneous use of condom for the male partner
  - b) simultaneous use of diaphragm with intravaginally applied spermicide and condom for the male partner starting at least 14 days prior to drug administration.
  - c) sterile male partner (vasectomized for at least 6 months)
  - d) Note: Surgically sterile subjects who have had a tubal ligation are considered of non-childbearing potential and are not required to use contraception
- 5) Willing to refrain from excessive use of alcohol during the entire study and willing to refrain from use of alcohol 24 hours prior to any PK blood draw taken during the study
- 6) Willing to refrain from use of prescription medications, over-the-counter medications and natural health products during the entire study
- 7) Willing and capable to give informed consent to participate in study

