**ADVERSE REACTIONS**

**Clinical Trials**

Estradiol levels may increase during the first weeks following the initial injection of LUPRON, but then decline to menopausal levels. This transient increase in estradiol can be associated with a temporary worsening of signs and symptoms (see **WARNINGS** section).

As would be expected with a drug that lowers serum estradiol levels, the most frequently reported adverse reactions were those related to hypoestrogenism.

The **monthly formulation of LUPRON DEPOT 3.75 mg** was utilized in controlled clinical trials that studied the drug in 166 endometriosis and 166 uterine fibroids patients. Adverse events reported in  $\geq 5\%$  of patients in either of these populations and thought to be potentially related to drug are noted in the following table.

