Adverse drug reactions (ADR) are defined in the ICH Guidance for Industry E2A: clinical safety data management: definitions and standards for expedited reporting as follows: “All noxious and unintended responses to a medicinal product related to any dose should be considered adverse drug reactions (ADR).” An ADR can therefore be any TEAE judged related to the medicinal product (causal relationship between a medicinal product and an AE is at least a reasonable possibility, i.e., the relationship cannot be ruled out).

In accordance with the prescribing information for Lupron Depot and other amenorrhea-inducing drugs, one category of ADR (represented by the PT “Menstrual Disorder”), may be analyzed as both TEAE and a metric of the menstrual bleeding pattern (e.g., a number of bleeding days during the dosing interval).

As an additional ADR analysis, incidence of subjects who experienced ADR will be presented by treatment group, by SOC, and PT, excluding the PT “Menstrual Disorder”.

The incidence of ADRs will be summarized for entire study and separately for the two study sub-periods (a 28-day dosing cycle and a 28-day post-dosing evaluation period) using the safety populations for any particular study subperiods. Each subject may only contribute once to each of the incidence rates, for an ADR following a given treatment, regardless of the number of occurrences. In summary table, SOC will be presented in descending order of overall incidence rate in terms of frequency of subjects and then in frequency of events (alphabetical order will be used in case of equal rates). For each SOC, PT will be presented the same way. Incidence of ADR (number of events) will also be presented by treatment, SOC, and PT.

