## 11.2 Statistical Analyses

Individual and mean concentration of hormonal levels versus nominal time curves will be presented by treatment group for each evaluation timepoint. Descriptive statistics (sample size “n”, mean, standard deviation, coefficient of variation, median, minimum value and maximum value) of hormonal levels will be presented for each timepoint.

Summaries of the LH, FSH,  $E_2$ , and progesterone levels will be reported for each dosing and post-dosing evaluation timepoint, for the dosing days 22 and 28 (Day 29 for Treatments “C” and “D”) (combined: i.e. the maximum among the 2 values) and, optionally, for the entire 28-day dosing period and the entire post-dosing Evaluation Period. Changes from pre-dosing baseline in LH, FSH,  $E_2$  and progesterone levels will also be summarized (sample size “n”, mean, standard deviation, median, minimum value and maximum value) at each on-treatment evaluation timepoint. Pre-dosing baseline for all PD metrics is the highest value across two observations: (a) screening measurement and (b) measurement taken just prior to the first dose of the study drug. Similar summaries will be provided for the follow-up visits (postdosing Days 7, 14, 21, and 28). In addition, time to return to pre-study baseline hormonal levels could be estimated.

Summaries of PD metrics may be further stratified by the cycle period (days) of the start of dosing. Categorical variables will be summarized by using frequency counts and percentages for each treatment by visits involved. In addition, the number of patients with missing values will be displayed.

Additionally, correlations between leuprolide concentration levels and PD parameters will be examined graphically. PD parameters may include LS, FSH, E2 and progesterone levels. These evaluations will not be performed for Treatment “D”.

Number of vaginal (menstrual) bleeding days will be summarized by treatment group for 28 days of therapy and for 28 days of post-study follow-up. The subject incidence of the onset of menstrual period after completion of therapy will be reported for each treatment group.

The onset of menstrual period is defined as at least three consecutive bleeding/spotting days during the 28-day postdosing period.

Additional PD analyses could be performed if necessary.

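### In Treatment D the on-therapy bleeding-day count is nearly the same with or without menstrual suppression, if the menses due on Days 6-10 still occurs

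*Protocol*

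**What the plan says.** The Protocol Synopsis (PD Parameters) and Section 12.3 plan the bleeding summary as follows: "Number of vaginal (menstrual) bleeding days will be summarized by treatment group for 28 days of therapy and for 28 days of poststudy follow-up". SAP 11.2 repeats it: "Number of vaginal (menstrual) bleeding days will be summarized by treatment group for 28 days of therapy and for 28 days of post-study follow-up". Both also report, by group, how many women have a menstrual period begin after therapy ends. SAP 11.2 defines that onset as three or more consecutive days of bleeding or spotting in the postdosing period. Breaking PD summaries down by the cycle day at first dose is optional in both documents.

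SAP 9.2, in a paragraph that refers to drugs that induce amenorrhea, says menstrual disorder may be analyzed both as a TEAE and as "a metric of the menstrual bleeding pattern (e.g., a number of bleeding days during the dosing interval".

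Start of dosing depends on the group. Treatment D women "will have a dosing initiation visit scheduled 5-9 days before the anticipated start of their next menstrual cycle". Treatments A-C start on cycle days 1-4 or in the last 11 days of the cycle (Synopsis and Appendix G). Eligibility requires: "Regular menstrual cycles with a usual length ranging from 21 days to 35 days". Screening records the last menstrual period and "menstrual pattern (typical duration of a menstrual cycle and typical duration of a menstrual period", and daily bleeding diaries cover both 28-day periods.

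**The concern.** A count of bleeding days over a fixed 28-day window can reveal suppression only if the window contains a menses that the drug could have prevented. Treatment D begins shortly before a menses, so that menses falls early in the window and the next one is a full cycle later. If the early menses occurs regardless of drug effect, a suppressed and an unsuppressed D woman record about the same on-therapy total. A D group with full suppression could then be read as still menstruating on treatment.

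The start windows also differ between D and A-C, so a difference in on-therapy totals between groups can come from cycle phase alone.

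**Working it through.** The plan gives no figure to reproduce. The check is calendar arithmetic over every permitted start day and cycle length.

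**Inputs.** Cycle length L = 21 to 35 days (Protocol 8.1). Onset of menses is cycle day 1 (Synopsis). Treatment D starts k = 5 to 9 days before expected menses. A-C start on cycle day d = 1 to 4 (early) or d = L-10 to L (late). The late rule reproduces Appendix G: days 11-21 at L = 21, 18-28 at L = 28, 25-35 at L = 35. Protocol 7.1 and SAP 3.3 give days 18-28 for everyone, which agrees with Appendix G only at L = 28; those passages need reconciling. Appendix G is used here.

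**Treatment D.**
- First menses: Day k+1, so Days 6-10.
- Next menses: Day k+1+L, from 5+1+21 = Day 27 to 9+1+35 = Day 45. For L = 28 it is Days 34-38.
- Onset by Day 28 requires k+L ≤ 27. Only (k, L) = (5, 21), (6, 21) and (5, 22) qualify: 3 of 15 × 5 = 75. They start on Days 27, 28 and 28, adding 2, 1 and 1 countable days.
- The other 72 (96%) start on Days 29-45, which are postdosing Days 1-17.

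**A-C, late start.**
- First menses: Day L-d+2, so Days 2-12.
- Next menses: Day 2L-d+2, so Days 23-47.
- By Day 28 in 6+5+4+3+2+1 = 21 of 15 × 11 = 165 (L = 21 to 26; none at L = 28). The other 144 have no second menses on therapy.

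**A-C, early start.**
- Next menses: Day L+2-d, so Days 19-36.
- By Day 28 when L ≤ 26+d: 7+8+9+10 = 34 of 15 × 4 = 60 (57%).
- At L = 28 and an assumed 5-day menses, the second menses starts on Days 29, 28, 27, 26 for d = 1 to 4. The difference between no effect and full suppression is then 0, 1, 2 or 3 days.

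**Comparability.** With the same 5-day menses, a fully suppressed early starter still records the rest of the period under way: 6-d days, that is 5, 4, 3 or 2. A fully suppressed D woman whose due menses occurs records 5. Start phase alone can separate the groups by up to 3 days.

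**Sensitivity for D.** Counting the first menses as Day k instead of k+1 gives 6 of 75 (8%) with a second onset by Day 28. The combinations are unweighted because the documents give no distribution of cycle length. Simulation under assumed variation gave:
- mean cycle 28 days, between-woman SD 2-4 days, per-cycle error SD 0-3 days: 0.1% to 9% with a second onset by Day 28, about 0 to 1.1 of 12 women;
- cycle lengths uniform on 21-35 days, same error: 4% to 12%, about 0.5 to 1.4 of 12.

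**The case against.** The strongest reply is that the plan already covers the days in question. Follow-up runs over Days 29-56, and in 72 of 75 combinations D's second menses is due inside it (with a 5-day menses it ends by Day 49). No measurement is missing, and that part stands. What remains is interpretation: the planned onset variable counts any three-day bleed after therapy, so an unsuppressed woman menstruating on schedule scores the same as a suppressed woman who has recovered.

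Second, no passage makes the on-therapy count the test of suppression. The primary PD metric is E2 at or below 40 pg/mL, the study is descriptive, and SAP 9.2 offers the count only as an example. This stands and limits the weight of the point.

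Three stronger readings are tempting, and the documents do not support them:
- *That the first menses is fixed whatever the drug does.* The appended label says "Estradiol levels may increase during the first weeks following the initial injection of LUPRON, but then decline to menopausal levels", which supports this only indirectly. The label also reports amenorrhea of 74% after the first month (endometriosis) and 61% in the first month (fibroids). Neither figure states the cycle phase at first dose, so they neither confirm nor refute the premise. If the drug prevents or shortens the due menses, the on-therapy count would show it.
- *That the count cannot show suppression in any group.* The 34 of 60 early-start combinations contradict this.
- *That removing menstrual disorder hides a safety signal.* It is removed only from the additional ADR table; the main TEAE tables keep it.

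Finally, expected dates rest on self-reported cycle length, which after recent hormonal contraception may be historical. That is a real limitation of any remedy.

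**Conclusion.** The point holds for Treatment D and for most late starters in A-C, conditional on the due menses still occurring. Under that assumption the on-therapy total changes by 0 days in 72 of 75 D combinations and by 1-2 days in the other three, comparing an unaltered cycle with no bleeding after the first menses. That all-or-nothing comparison ignores changed duration and unscheduled spotting.

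The non-comparability of D with A-C follows from the different start windows, and the optional breakdown by start phase does not ensure it is dealt with. The weakness lies in how the on-therapy and post-therapy summaries would be read, not in data collection. Because the endpoint is descriptive and secondary to E2 suppression, the change is worth making but does not affect the study's main conclusion.

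**What to change.** Amend SAP 11.2 as follows.

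- (a) From last menstrual period, typical cycle length and diary data, derive each woman's expected menses dates. Report separately the first menses due after the first dose, and whether the second expected menses occurred by its expected date. Give the delay in days, counted across the Day 28/29 boundary and censored at the woman's last diary day (Day 56 for completers).
- (b) Make the breakdown of bleeding summaries by cycle phase at first dose mandatory.
- (c) Keep the raw 28-day totals, and state that the on-therapy total alone is not evidence for or against menstrual suppression in Treatment D or in late starters.

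The cost is SAP wording and a small set of derived variables from data already collected. Expected dates can be off by a few days, and some delays will be censored. With up to 12 women in D, individual dates should be listed beside the summary.

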## 5. BACKGROUND

Enteris BioPharma has developed a proprietary Oral Peptide Delivery Technology to enable, for the first time, the oral administration of the widely-prescribed gonadotropin-releasing hormone agonist leuprolide, a synthetic nonapeptide.

Various formulations of leuprolide at several different dose levels have been previously approved by the FDA for treatment of prostate cancer, endometriosis, uterine fibroids, and central precocious puberty. Specifically, approval of leuprolide for the treatment of endometriosis has been granted for both 3.75 mg q 1 month and 11.25 mg q 3 months as intramuscular (IM) injections (Lupron Depot® and Lupaneta®, the latter including co-packaging of leuprolide with daily oral norethindrone acetate 5 mg).

Enteris now develops a daily oral form of leuprolide (Leuprolide Oral Tablet) for the treatment of endometriosis. The prospect of delivering this drug orally would allow the elimination of IM injections associated with disturbing side effects. In addition, an oral route of delivery may offer a number of other potential clinical benefits (*eg*, a possibility of immediate termination of therapy for medical or any other reasons).

The name of the product (Leuprolide Oral Tablet) contains the name of the active moiety (Leuprolide), and not the name of the salt (Leuprolide Acetate), as stipulated by the USP Salt Policy and FDA Guidance for Industry titled, “Naming of Drug Products Containing Salt Drug Substances.” The strength is also expressed in terms of the active moiety (*e.g.*, “4 mg Leuprolide Oral Tablets”) rather than the salt strength equivalent (*e.g.*, “4.46 mg Leuprolide Acetate Oral Tablets”).

Because of the well-documented pharmacology, clinical efficacy and safety of leuprolide for this and other indications, the clinical development of this new oral dosage form will be ultimately linked to pharmacokinetic (PK) and pharmacodynamic (PD) properties of marketed leuprolide formulations, including but not limited to IM depot form (“Lupron Depot”) which will serve as reference product(s) in the Enteris BioPharma’ 505(b)(2) NDA. Particularly, the PK exposure and safety profile of Leuprolide Oral Tablets will be evaluated against the marketed 1-mg subcutaneous (SC) injection. Extensive nonclinical safety data, and clinical safety and efficacy data exist from publicly available sources.

Leuprolide Oral Tablets were shown to be safe and well tolerated in the Phase 1 study LOPDT-PH1-01, at doses of 1 and 4 mg in normal healthy volunteers. The absolute bioavailability was 2.2% and 3.0% for the 1 and 4 mg doses, respectively, compared to subcutaneous injection. The 4-mg Leuprolide Oral Tablet generated an overall drug exposure (a 24-hour AUC=19338 h\*pg/mL) that was less than 12% of the drug exposure (163021 h\*pg/mL) reported for a marketed 1-mg SC injection. A projected AUC for the 10 mg tablet administered twice daily (Treatment “D”) will be less than 60% of the 1-mg SC drug exposure. Projected Cmax of Treatment “D” will also be lower than Cmax reported for the 1-mg SC injection. These estimates clearly support the safety of the 10 mg tablet administered twice daily (Treatment “D”).

Following the conclusion of LOPDT-PH1-01, Leuprolide Oral Tablets were reformulated in an effort to increase bioavailability. Reformulated tablets were administered to beagle dogs and the bioavailability was compared to the 4 mg dose from LOPDT-PH1-01. An increase in bioavailability was seen, from 2.2% for the Phase 1 tablet to 7.3% for the reformulated tablet. The reformulated 4 mg tablet (LEU-

012-17002) was then tested in this study, with 28 days of dosing in QD and BID regimens (Treatments “A” and “B”, respectively), and Lupron Depot 3.75 mg as an active comparator (Treatment “C”). Interim PK/PD results from this study were recently evaluated, which showed that the bioavailability of the reformulated tablet, rather than increase as predicted by testing in the dog, actually decreased to approximately 1.5%. Pharmacodynamic data, specifically the suppression of estradiol, showed that both the 4 mg QD and BID regimens fell substantially short of the suppression demonstrated by Lupron Depot®. Interim safety results from this study were also evaluated. Overall, Leuprolide Oral Tablets within a 4 mg to 8 mg daily dosing range were safe and reasonably well tolerated. The study results support a further dose increase in planned clinical evaluations.

This protocol amendment include a fourth arm, which will be a 10 mg Leuprolide Oral Tablet administered BID for 28 days (Treatment “D”). As with the previous arms of the study, PD markers will be evaluated weekly during the 28 days of dosing and for a 28 day wash out period. The tablet formulation will revert to the more successful formulation used in the Phase 1 study, where the bioavailability was 3.0%. The amount of leuprolide projected to be absorbed into the circulation is 0.6 mg per day (3% of 20 mg). This is roughly equivalent to the 0.5 mg per day delivered by daily subcutaneous injection that was effective in treating uterine fibroids, and is approximately 60% of the 1 mg approved SC dose administered in the Phase 1 study. There is a further safety margin for the Treatment “D” dose of 10 mg bid: the Lupron Depot® 3.75 mg label contains the statement, “In early clinical trials using daily subcutaneous leuprolide acetate in patients with prostate cancer, doses as high as 20 mg/day for up to two years caused no adverse effects differing from those observed with the 1 mg/day dose.” Given the low bioavailability of the oral dose, about 3%, a substantial safety margin is assured.

The comparative PK/PD evaluations will form important bridges between different routes of leuprolide administration using both the company’s proprietary data and relevant published findings.

Additional information on Leuprolide Oral Tablet can be found in the Investigator's Brochure.

